5. PARTICIPANT SELECTION

5.1. Allocation of Slots to Study Sites

This is an investigator-initiated trial with intended single-site enrollment limited to patients enrolling at Vanderbilt University.

5.2. Inclusion Criteria

Patients must meet all of the following inclusion criteria to be eligible for enrollment into the study:

1. Signed and dated written informed consent.
2. Male or female \geq 18 years of age.
3. Eastern Cooperative Oncology Group (ECOG) performance status 0 or 1.
4. Histologically confirmed adenocarcinoma of the small intestine that is advanced (not amenable to surgery) or metastatic (clinical stage IV). For the purposes of this study, ampullary tumors are considered a part of the duodenum and are classified as adenocarcinomas of the small intestine.
5. At least one measurable lesion as defined by Response Evaluation Criteria in Solid Tumors (RECIST) version 1.1 criteria (Appendix 1) that has not been previously irradiated and which can be followed by CT or MRI.
6. Adequate organ function including:

- Absolute neutrophil count (ANC) $\geq 1.5 \times 10^9/L$
 - Platelets $\geq 100 \times 10^9/L$
 - Hemoglobin $\geq 9/g/dL$ (may have been transfused)
 - Total serum bilirubin ≤ 1.5 times upper limit of normal (ULN)
 - Aspartate aminotransferase (AST/SGOT) and alanine aminotransferase (ALT/SGPT) $\leq 2.5 \times ULN$ (or $\leq 5 \times ULN$ if liver metastases are present)
 - Serum creatinine $\leq 1.5 \times ULN$ or estimated creatinine clearance ≥ 30 mL/min as calculated using the Cockcroft-Gault (CG) equation (Appendix 3).
7. Archival tissue [paraffin block(s) or unstained slides from paraffin block(s)] from the primary tumor and/or a metastatic site judged reasonably available prior to initiating treatment, or willingness to undergo fresh pre-treatment tumor biopsy. (Prior to initiating treatment, the screening team must have documentation that an archival or fresh tumor specimen has been requested from a local or outside facility. However, physical possession of requested tissue or waiting for histological analysis or confirmation that an acquired specimen contains tumor tissue sufficient for analysis is not a requirement prior to initiating treatment.) If no archival tissue is available and patient consents to a fresh biopsy, but the patient's lesion is deemed inaccessible to safe biopsy, the patient will be allowed to enroll if otherwise eligible.
8. Female patients of childbearing potential and male patients able to father children who have female partners of childbearing potential must agree to use one highly effective method (defined as less than 1% failure rate per year) and one additional effective method of contraception (Appendix 4) from 15 days prior to first trial treatment administration until at least 30 days after study participant's final dose of avelumab. Females of childbearing potential are defined as those who are not surgically sterile or post-menopausal (i.e. patient has not had a bilateral tubal ligation, a bilateral oophorectomy, or a complete hysterectomy; or has not been amenorrheic for 12 months without an alternative medical cause). Post-menopausal status in females under 55 years of age should be confirmed with a serum follicle-stimulating hormone (FSH) level within laboratory reference range for postmenopausal women.
- Male patients able to father children are defined as those who are not surgically sterile (i.e. patient has not had a vasectomy).
9. Serum pregnancy test (for females of childbearing potential) negative at screening.
10. Re-enrollment of a subject that has discontinued the study as a pre-treatment screen failure (i.e. a consented patient who did not receive avelumab) is permitted. If re-enrolled, the subject must be re-consented. Only the screening procedures performed outside of protocol-specified timing must be repeated.

5.3. Exclusion Criteria

Patients will be ineligible for enrollment into the study if they meet any of the following criteria:

1. There is no restriction on the number of prior therapies. However, prior therapy with antibody or drug specifically targeting T cell regulatory proteins, including but not limited to the following is not allowed: Prior immunotherapy with IL-2 or IFN- α , or an anti-PD-1

(including nivolumab), anti-PD-L1, anti-PD-L2, anti-CD137, or anti-cytotoxic T-lymphocyte-associated antigen-4 (CTLA-4) antibody (including ipilimumab), or any other antibody or drug specifically targeting T-cell co-stimulation or checkpoint pathways.

2. Within 28 days before first dose of avelumab:
Anti-cancer treatment, major surgery requiring general anesthesia, or the use of any investigational agent.
3. Within 14 days before first dose of avelumab:
Therapeutic or palliative radiation therapy. (Subjects receiving bisphosphonate or denosumab are eligible provided treatment was initiated at least 14 days before the first dose of avelumab.)
4. Current use of immunosuppressive medication, except the following:
 - Subjects are permitted the use of corticosteroids with minimal systemic absorption (e.g. topical, intra-articular, intranasal, and inhaled);
 - Systemic corticosteroids at physiologic doses ≤ 10 mg/day of prednisone or equivalent are permitted;
 - A brief (less than 3 weeks) course of corticosteroids for prophylaxis (e.g. CT scan premedication against contrast dye allergy) or for treatment of non-autoimmune conditions (e.g. delayed-type hypersensitivity reaction caused by a contact allergen) is permitted.
5. Previous malignant disease other than adenocarcinoma of the small intestine within the last 5 years, with the exception of basal or squamous cell carcinoma of the skin or cervical carcinoma in situ considered curatively treated (i.e. complete remission achieved at least 2 years prior to first dose of avelumab AND additional therapy not required while receiving study treatment).
6. All subjects with brain metastases, expect those meeting the following criteria:
 - Brain metastases that have been treated locally and are clinically stable for at least 2 weeks prior to enrollment
 - No ongoing neurological symptoms that are related to the brain localization of the disease (sequelae that are a consequence of the treatment of the brain metastases are acceptable.
 - Subjects must be either off steroids or on a stable or decreasing dose of ≤ 10 mg daily prednisone (or equivalent)
7. Receipt of any organ transplantation including allogeneic stem-cell transplantation.
8. Significant acute or chronic infections requiring systemic therapy.
9. Known history of testing positive for human immunodeficiency virus (HIV), or acquired immunodeficiency syndrome (AIDS).

10. Hepatitis B virus (HBV) or Hepatitis C virus (HCV) infection at screening (positive HBV surface antigen or HCV RNA if anti-HCV antibody screening test positive).
11. Active autoimmune disease with reasonable possibility of clinically significant deterioration when receiving an immuno-stimulatory agent. Subjects with Type 1 diabetes mellitus, vitiligo, psoriasis, hypo- or hyperthyroid disease not requiring immunosuppressive treatment are eligible.
12. Interstitial lung disease that is symptomatic or which may interfere with the detection or management of suspected drug-related pulmonary toxicity.
13. Uncontrolled asthma [defined as having 3 or more of the following features of partially controlled asthma within 28 days prior to starting study treatment: Daytime symptoms more than twice per week, any limitation of activities, any nocturnal symptoms/awaking, need for reliever/rescue inhaler more than twice per week, or known lung function (PEF or FEV1) without administration of a bronchodilator that is < 80% predicted or personal best (if known)].
14. Current symptomatic congestive heart failure (New York Heart Association \geq class II), unstable cardiac arrhythmia requiring therapy (e.g. medication or pacemaker), unstable angina (e.g. new, worsening or persistent chest discomfort), or uncontrolled hypertension (systolic > 160 mmHg or diastolic > 100mmHg). Or any of the following occurring within 6 months (180 days) prior to first dose of avelumab: Myocardial infarction, coronary/peripheral artery bypass graft, cerebrovascular accident or transient ischemic attack, or serious cardiac arrhythmia requiring medication. (Use of antihypertensive medication to control blood pressure is allowed.)
15. Concurrent treatment with a non-permitted drug (see Section 10).
16. Requirement of anticoagulant therapy with oral vitamin K antagonists such as Coumadin (warfarin). Low-dose anticoagulants for the maintenance of patency in a central venous access device or the prevention of deep vein thrombosis or pulmonary embolism is allowed. Therapeutic use of low molecular weight heparin is allowed.
17. Persisting toxicity related to prior therapy that has not reduced to Grade 1 [National Cancer Institute Common Toxicity Criteria for Adverse Events (NCI CTCAE) version 4.03]; however, alopecia and sensory neuropathy Grade \leq 2 is acceptable.
18. Known severe (Grade \geq 3 NCI-CTCAE v4.03) hypersensitivity reactions to monoclonal antibodies, including hypersensitivity to the investigational agent or any component in its formulations, or history of anaphylaxis.
19. Vaccination within 28 days of the first dose of avelumab and while on trial is prohibited, except for administration of inactivated vaccines (for example, inactivated influenza vaccine).
20. Pregnant or breastfeeding females.

21. Known alcohol or drug abuse
22. Prisoners or subjects who are involuntarily incarcerated.
23. Other severe acute or chronic medical condition, including immune colitis, inflammatory bowel disease, immune pneumonitis, pulmonary fibrosis, or psychiatric condition including recent (within the past year) or active suicidal ideation or behavior; or laboratory abnormalities that may increase the risk associated with study participation or study treatment administration or may interfere with the interpretation of study results and, in the judgment of the investigator, would make the patient inappropriate for entry into this study.

5.4. Inclusion of Underrepresented Populations

Women and men of all races and ethnic groups are eligible for this trial. There is no bias towards gender, age, or race in the clinical trial outlined.

5.5. Number of Patients and Replacement of Patients Who Discontinue Early

Approximately 25 patients evaluable for response are anticipated to enroll in this study at Vanderbilt University Medical Center.

In general, it is intended that patients will be treated until disease progression or intolerable toxicity. The criteria for patient discontinuation are listed in Sections 9 and 11.

If a patient discontinues study treatment for reasons clearly not related to study treatment, after completing fewer than one planned infusion of avelumab, and/or receiving <75% of the total intended dose of avelumab over the first cycle of treatment + an additional 14 days (i.e. first 28 days after initiating patient's first dose of avelumab), then that patient will be considered not evaluable for response to study treatment and may be replaced with a new patient.

6. REGISTRATION PROCEDURES

6.1. Registration

All patients MUST be registered with the VICC prior to the start of protocol treatment. Registration can only be conducted during the business hours of 8AM – 5PM Central Standard Time Monday through Friday.

- 1) All sites must email the VICC CTSR Coordinating Center at [contact] to notify of upcoming registration and ensure slot availability. The following information should be included in your email:
 - Study number
 - Patient initials
 - Disease type
 - Anticipated consent date

- Anticipated start date
- 2) Email the following documents to the Coordinating Center for eligibility review and patient enrollment ([contact]):
- Copy of the patient's signed and dated Informed Consent, including documentation of the consent process.
 - Patient Enrollment Form
 - Eligibility supporting documents such as pathology reports, laboratory tests, etc. *or* EMR access. Note: all source documents should be de-identified and screening/subject ID number added prior to sending.
 - Signed and completed Eligibility Checklist. **To be eligible for registration to the study, the participant must meet each inclusion and exclusion criterion listed in the eligibility checklist.**

Note: All study documents should be received 24-48 hours prior to the patient's anticipated start date. Same day treatment registrations will only be accepted with prior notice and discussion with the Coordinating Center. Please email the Coordinating Center if enrollment is needed sooner.

Upon satisfactory review of eligibility documents submitted, the Coordinating Center will approve enrollment and issue a subject ID number if one was not issued at screening. Once registration/enrollment confirmation from Coordinating Center is received, proceed with protocol procedures.

Please contact the assigned Study Contact with any questions regarding this process. You can also reach out to your assigned Clinical Research Associate (CRA) once the study is activated.

The VICC Coordinating Center will assign Subject ID numbers to all patients whose eligibility has been confirmed. Only patients deemed eligible will be registered to investigational treatment. Following registration, eligible participants should begin study treatment consistent with the protocol no later than 28 days after registration/enrollment by the VICC Coordinating Center. If a participant does not receive protocol therapy following registration within the allowed time period, the participant's registration on the study will be canceled. The Study Contact should be notified of cancellations as soon as possible. Patients being re-screened will need to consent to repeated procedures. As such, the Coordinating Center will require a new, signed Informed Consent document.

Issues that would cause treatment delays should be discussed with the Protocol Chair.

As is generally accepted, standard of care procedures performed prior to consent, but within the protocol defined screening window for each assessment, can be used for study purposes. All research-only procedures must be performed after patient consent.

7. SCHEDULE of ASSESSMENTS

7.1. Study Calendar

Protocol Activities	Screening ≤ 28 Days Prior to First Dose	Day 1 of Cycles ≥ 1 Every 14 days (+3 days)¹¹	Post Treatment	
			EOT/ Withdrawal ¹⁴	Follow-Up ¹⁷
Clinical Assessments				
Consent, Medical History & Demographics	X			
Physical Examination and ECOG	X	X ⁹	X	X ¹⁶
Vital Signs ¹	X	X ¹	X	X ¹⁶
Con Meds & Adverse Events	X	X ⁹	X	X ¹⁶
Height and Weight ²	X	X ²	X	
Survival Follow-up				X ¹⁸
Laboratory Studies				
Hematology and Blood Chemistry ³	X	X ¹⁰	X	X ¹⁶
HCV and HBV Testing	X			
Serum Pregnancy Test ⁴	X	X ⁴	X	
Free T4 and Thyroid Stimulating Hormone (TSH)	X	X ⁵	X	X ⁵
Tumor and Pharmacogenetic Assessments				
CT or MRI Scans ⁶	X ⁶	X ⁶	X ¹⁵	X ¹⁹
Archival Tumor Tissue	X ⁷			
Fresh Tumor Biopsy	X ⁸			
Pharmacogenetic Blood Sample		X ¹¹		
Treatment				
Avelumab infusion (10 mg/kg)		X ^{12,13}		

Notes:

- Vital signs to include heart rate, blood pressure and temperature (oral or tympanic). On days of each avelumab treatment: Pre-Dose and Post-Dose vitals should respectively be recorded ≤ 10 minutes prior to the start of the avelumab infusion (Pre), and ≤ 10 min after the end of the avelumab infusion (EOI). Following avelumab infusions, patients must be observed for 30 minutes post infusion for potential infusion related reactions.
- Height only at baseline. Weight within 3 days prior to every dose of avelumab. As per Note 11 below and protocol Section 8.2, avelumab dose must be adjusted if patient's weight changes $\pm 10\%$.
- Hematology to include: White blood count (WBC) with differential; hemoglobin, hematocrit and platelet count. Blood chemistry to include: Sodium, potassium, calcium, chloride, and bicarbonate; BUN, serum creatinine, glucose, total bilirubin, AST, ALT, alkaline phosphatase, total protein, and albumin.
- Serum pregnancy test required for females of childbearing potential, during Screening and on Cycle 1, Day 1 (unless already done within 72 hours prior to first dose of avelumab). Subsequent serum pregnancy tests to be done every 4 weeks on Day 1 of each cycle and at End of Treatment. Females of childbearing potential are defined as those not surgically sterile or not post-menopausal (i.e. patient has not had a bilateral tubal ligation, a bilateral oophorectomy, or a complete hysterectomy; or has not been amenorrheic for 12 months without an alternative medical cause). Postmenopausal status in females under 55 years of age should be confirmed with a serum follicle-stimulating hormone (FSH) level within laboratory reference range for postmenopausal women (if a patient's postmenopausal status is considered for childbearing potential and study required contraception).

5. Free T4 and TSH levels will be tested at screening, Cycle 3 Day 1, and then every 8 weeks while patients are on therapy. Free T4 and TSH levels will also be tested at EOT or at the Follow-up visit (if not performed in the previous 8 weeks).
6. Baseline evaluation of disease status by CT or MRI within 28 days prior to first dose of avelumab. Baseline and subsequent scans to include imaging of the chest, abdomen and pelvis. The first scheduled re-scan should be performed and evaluated 7 to 8 weeks after Cycle 1, Day 1 treatment, with subsequent scheduled scans intended every 8 to 9 weeks thereafter irrespective of dose delays. Thus, the first re-scan is anticipated during Week 2 of Cycle 4 (with evaluation prior to dosing on Cycle 5, Day 1). Additional re-scanning is anticipated during Week 2 of every 4th cycle (i.e. Week 2 of Cycles 8, 12, 16, etc) prior to infusion in the subsequent cycle (i.e. re-scanning prior to Day 1 of Cycles 5, 9, 13, 17, etc). Scanning on the same day as dosing is discouraged but allowed, provided scan results receive appropriate evaluation prior to study treatment (e.g. first re-scan is permitted on Cycle 5, Day 1, prior to treatment later that same day). Additional disease evaluations or increased scan frequency may be performed according to the medical judgment of the patient's study physician.
7. Archival tissue [paraffin block(s) or unstained slides from paraffin block(s)] from the primary tumor and/or a metastatic site judged reasonably available prior to initiating treatment, or willingness to undergo fresh pre-treatment tumor biopsy. Prior to initiating treatment, the screening team must have documentation that a paraffin block(s), unstained slides from a paraffin block(s), or a fresh biopsy has been requested from a local or outside facility. (However, physical possession of requested tissue, or waiting for histological analysis or confirmation that a certain number of acquired specimen slides are known to contain tumor tissue, is not a requirement prior to initiating treatment.) Please note: Archival or fresh biopsy should be excisional, incisional or core needle; fine needle aspiration is not sufficient. Patients without available or sufficient archival tumor samples (if otherwise eligible) will be allowed to participate, if they are willing to have a fresh biopsy of a primary or metastatic lesion. If no archival tissue is available and patient consents to a fresh biopsy, but the patient's lesion is deemed inaccessible to safe biopsy, the patient will be allowed to enroll if otherwise eligible.
8. In addition to the mandatory archival tissue or fresh tissue, an optional fresh biopsy will be requested from consenting subjects (including those with pre-existing archival tissue) with primary or metastatic lesion judged amenable to medically safe excisional, incisional or core needle biopsy.
9. On Cycle 1, Day 1: Physical exam (including ECOG performance status) and review of Con Meds and Adverse Events not required if already completed within 7 days prior to first dose of avelumab. After initiation of Cycle 4, physical exams may be performed monthly (i.e. after Cycle 4, Day 1 exam to confirm satisfactory completion of Cycle 3, the next regularly scheduled physical exam may occur 4 weeks later, on Cycle 6, Day 1; with subsequent monthly physical exams intended every even cycle, on Day 1 of Cycles 8, 10, 12, etc).
10. Hematology and blood chemistry must be collected prior to each avelumab dose, at the end of treatment visit, and at 30 days post-treatment safety follow-up.
11. Pharmacogenetic (PG) blood obtained once, prior to patient's first avelumab dose on Cycle 1, Day 1.
12. The avelumab dose will be 10 mg/kg administered as 1-hour intravenous (IV) infusion every 2 weeks (Q2W). Every effort should be made to target infusion timing to be as close to 1 hour as possible. However, given the variability of infusion pumps, time windows of -10 minutes and +20 minutes is permitted (i.e. scheduled avelumab infusion time is 60 minutes: -10 min/+20 min). See protocol Section 9 for recommended infusion pre-medications. Avelumab dosing will be based on the patient's weight in kilograms (kg). All patients should be weighed within 3 days prior to each avelumab dose. If a weight loss or gain $\geq 10\%$ is observed (compared to the weight used to calculate the immediately prior dose), then the amount of avelumab required for a current dose must be recalculated using the most recent weight obtained. Reduction of avelumab dose for toxicity management is not permitted, however avelumab administration may be held due to adverse events, as described in protocol Section 11.
13. Cycle 2, Day 1 dosing should occur 14 days after Cycle 1, Day 1. In the absence of delayed dosing (e.g. due to an adverse event), every reasonable effort should be made to remain on a consistent schedule of 14-day cycles; but for purpose of accommodating holidays, scheduling limitations, etc, subsequent cycles (i.e. Cycles 3+) may occur up to every 14 days +3 days. Consecutive doses of avelumab must be

- separated by no fewer than 14 days and, in the absence of adverse event management, no more than 17 days.
14. Reasonable effort should be made to complete End-of-Treatment / Withdrawal procedures on the day it is decided that a patient will no longer receive study treatment. These procedures must be completed subsequent to and not later than 21 days after a patient's final treatment with avelumab (and prior to any subsequent anti-cancer therapy).
 15. Unless already done within previous 28 days.
 16. A 1-month follow-up clinic visit is intended 28 days (± 7 days) after the preceding End-of-Treatment visit (at least 30 days after patient's final treatment with avelumab). Documented attempt(s) should be made for patient return to the study clinic. It will not be considered a protocol deviation if the patient is physically unable to return for the follow-up visit; such circumstance should be recorded in the study documents, and as much of the follow-up information as possible should be obtained via feasible patient contact and from local and outside facilities.
 17. Given the potential risk for delayed immune-related toxicities, safety follow-up must be performed up to 90 days (+3 days) after the last dose of avelumab administration. The extended safety follow-up beyond 30 days after last study drug administration may be performed either via a clinic visit or telephone call with a subsequent site visit requested in case any concerns noted during the telephone call.
 18. Each patient will be followed for survival every 3 months (± 14 days) after patient's final treatment with avelumab until death, end of the study, or until patient withdraws consent, whichever comes first. Contact can be made via clinic visit, chart review, obituary or similar observation (e.g. Social Security death index), or by telephone.
 19. If a patient discontinues the study for reason other than progressive disease confirmed by CT or MRI (e.g. adverse event), then CT or MRI scans of the chest, abdomen and pelvis should be continued every 8-9 weeks until disease progression is confirmed by imaging.

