7.6. Follow-Up Visit Assessments (30-Day and 90-Day)

A 1-month follow-up clinic visit is intended 28 days (± 7 days) after the preceding End-of-Treatment visit. Documented attempt(s) should be made for patient return to the study clinic. It will not be considered a protocol deviation if the patient is physically unable to return for the follow-up visit; such circumstance should be recorded in the study documents, and as much of the follow-up information as possible should be obtained via feasible patient contact and from local and outside facilities.

Documented attempts should be made to have patients return to the clinic 28 days (± 7 days) after the prior End-of-Treatment visit (at least 30 days after patient's final treatment with avelumab), in order to undergo the following assessments:

- Physical exam
- ECOG Performance Status
- Concomitant Medications and Adverse Events
- CBC and Serum chemistry
- Free T4 and Thyroid stimulating hormone (TSH) if not performed in the previous 8 weeks.

If a patient discontinues the study for reason other than progressive disease confirmed by CT or MRI (e.g. adverse event), then CT or MRI scans of the chest, abdomen and pelvis should be continued every 8-9 weeks until disease progression is confirmed by imaging.

Given the potential risk for delayed immune-related toxicities, safety follow-up must be performed up to 90 days (+3 days) after the last dose of avelumab administration.

The extended safety follow-up beyond 30 days after last study drug administration may be performed either via a site visit or via a telephone call with subsequent site visit requested in case any concerns noted during the telephone call.

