14.1. General

Safety assessments will consist of monitoring and reporting AEs and SAEs that are considered possibly, probably or definitely related to avelumab, all events of death, and any study-specific issue of concern.

Adverse event collection and reporting is a routine part of every clinical trial. Each adverse event will be graded according to the NCI's Common Terminology Criteria for Adverse Events (NCI CTCAE), Version 4.03, dated June 14, 2010, currently locatable via the following URL:

< http://evs.nci.nih.gov/ftp1/CTCAE/CTCAE_4.03_2010-06-14_QuickReference_8.5x11.pdf >.

For events not listed in the CTCAE, severity will be designated as mild, moderate, severe or life threatening, or fatal which respectively correspond to Grades 1, 2, 3, 4, and 5 on the NCI CTCAE, with the following definitions:

- **Mild:** An event not resulting in disability or incapacity and which resolves without intervention;
- **Moderate:** An event not resulting in disability or incapacity but which requires intervention;
- **Severe:** An event resulting in temporary disability or incapacity and which requires intervention;
- **Life-threatening:** An event in which the patient was at risk of death at the time of the event;
- **Fatal:** An event that results in the death of the patient.

Information on all adverse events, whether serious or not, whether reported by the participant, directly observed, or detected by physical examination, laboratory test or other means, will be collected, recorded, followed and reported as described in the following sections.

Reporting period: Adverse events experienced by participants will be collected and reported from initiation of study medication, throughout the study, and within 30 days of the last dose of study medication. Participants who experience an ongoing adverse event related to a study procedure and/or study medication beyond 30 days will continue to be contacted by a member of the study team until the event is resolved, stabilized, or determined to be irreversible by the participating investigator.

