14.3. Safety Parameters and Definitions

14.3.1 Adverse Event (AE)

An AE is any unfavorable and unintended sign, symptom, or disease temporally associated with the use of an investigational medicinal product (IMP) or other protocol-imposed intervention, regardless of attribution. Progressive disease will not be considered an adverse event.

An adverse event includes the following:

- AEs not previously observed in the patient that emerge during the protocol-specified AE reporting period, including signs or symptoms that were not present prior to the AE reporting period.
- Complications that occur as a result of protocol-mandated interventions (e.g. invasive procedures such as biopsy).
- If applicable, AEs that occur prior to assignment of study treatment associated with medication washout, no treatment run-in, or other protocol-mandated intervention.
- Pre-existing medical conditions (other than the condition being studied) judged by the investigator to have worsened in severity or frequency or changed in character during the protocol-specified AE reporting period.
- Abnormal laboratory values or diagnostic test results constitute adverse events only if they induce clinical signs or symptoms or require treatment or further diagnostic tests.

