14.5.10 Post-Study Adverse Events

The investigator should expeditiously report any SAE occurring after a patient has completed or discontinued study participation if attributed to prior avelumab exposure. If the investigator should become aware of the development of cancer or a congenital anomaly in a subsequently conceived offspring of a female patient who participated in the study, this should be reported as an SAE.

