14.5.12 Adverse Events of Special Interest (AESIs)

Any adverse event that is suspected to be a potential immune-related adverse event (irAE) is considered an AE of special interest (AESI). Specific guidance for the management of irAEs is provided in Section 11.7. AESIs are reported according to the general AE reporting rules specified in Section 14.5.

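### Adverse-event collection stops 30 days after the last dose, although safety follow-up runs to day 90 for delayed immune toxicity, so a new non-serious immune event on days 31–90 can drop out of the primary safety summary.

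*Combined protocol and SAP*

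**What the plan says.** Day 0 is the last dose throughout.

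- **Collection period (14.1).** Adverse events are "collected and reported from initiation of study medication, throughout the study, and within 30 days of the last dose of study medication". Beyond 30 days the text provides for continued contact only about ongoing events related to a study procedure or the drug.
- **What counts (14.3.1).** The list of included events has "AEs not previously observed in the patient that emerge during the protocol-specified AE reporting period".
- **Immune-related events (14.5.12).** Any suspected immune-related adverse event (irAE) is an event of special interest, and "AESIs are reported according to the general AE reporting rules specified in Section 14.5". No separate collection period is given.
- **Follow-up (7.1 Note 17 and 7.6).** "Given the potential risk for delayed immune-related toxicities, safety follow-up must be performed up to 90 days" (+3) after the last dose, by clinic visit or telephone.
- **1-month visit (7.1 Note 16 and 7.6).** It is set 28 (±7) days "after the preceding End-of-Treatment visit (at least 30 days after patient's final treatment with avelumab"), and its list includes "Concomitant Medications and Adverse Events".
- **After participation (14.5.10).** The investigator reports "any SAE occurring after a patient has completed or discontinued study participation if attributed to prior avelumab exposure".
- **Concomitant medication (10.1).** Recording ends 30 days after treatment.
- **Analysis (17.3).** All adverse events are summarized by patient. No post-dose window is named.
- **End of treatment (7.1 Note 14 and 7.5).** "These procedures must be completed subsequent to and not later than 21 days after a patient's final treatment with avelumab". Note 14 also asks for reasonable effort to hold the visit on the day the decision to stop is made.
- **Holds (11.1).** A hold may last 28 days, counted from the last dose, before treatment must be stopped for good, subject to cross-referenced exceptions.

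**The concern.** The plan keeps patients under safety follow-up for 90 days because immune toxicity can appear late, but its collection rule for new events ends at day 30. A Grade 2 thyroid, skin or bowel event that starts on day 50 and is managed without admission is the kind of event the extended follow-up exists to find. On the 30-day rule it is not a reportable adverse event of the study, and nothing in 17.3 brings it into the tables.

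Describing safety is one of the two primary objectives in 3.1. If such events are left out, the reported irAE incidence is too low for the follow-up the plan itself requires. If some staff record them and others do not, the rate depends on how 14.1 was read.

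**Working it through.** **1. The periods side by side.**

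| Item | Source | Ends, in days after last dose |
|---|---|---|
| New adverse events | 14.1 | 30 |
| Concomitant medication | 10.1 | 30 |
| Required safety follow-up | Note 17, 7.6 | 90 (+3) |
| Analysis window | 17.3 | not stated |

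Days 31 to 90 are 90 − 30 = 60 days, or 60/90 = 67% of the required follow-up; with the 3-day allowance, 63 days.

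**2. Where an event with onset on days 31–90 goes.**

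- Serious and attributed to avelumab: 14.5.10 provides for a report once participation has ended.
- Already ongoing and related at day 30: followed under 14.1.
- New, non-serious and suspected immune-related: 14.1 has closed, the item quoted from 14.3.1 points back to the reporting period, and 14.5.12 states no longer period.

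In the Study Calendar, the adverse-event row in the follow-up column carries Note 16, the 1-month visit. It does not schedule adverse-event recording at the day-90 contact.

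**3. Size.** Assume the safety summary has 25 patients; the actual number may differ slightly, because 17.3 requires at least one cycle or a stop for a treatment-related event. Let k be the number of patients whose only event of a given type starts on days 31–90. The understatement is k/25 = 4k percentage points. Table 3 gives 95% limits for k of 25. It was written for response, but the same interval applies to any proportion of 25. If no event of that type starts by day 30, the report would show 0 of 25 with upper limit 13.3%, whereas the count including late onsets would be:

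| k | Incidence | Upper limit (Table 3) |
|---|---|---|
| 0 | 0% | 13.3% |
| 1 | 4% | 19.5% |
| 2 | 8% | 25.0% |
| 3 | 12% | 30.0% |

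The documents give no onset times for irAEs, so k cannot be estimated and may be zero.

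**4. The response rule.** The plan states 80% power for 4 or more responses in 25 at a true rate of 21% against 5%. The exact binomial gives power 80.1% and one-sided type I error 3.4%, so the plan's figure reproduces. Neither depends on the adverse-event period.

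**5. End-of-treatment limit (secondary).** Both clocks start at the last dose. A stop forced because a hold has passed 28 days is decided on day 29 at the earliest, 29 − 21 = 8 days past the limit. A decision on days 22–28 also misses it.

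**The case against.** The strongest reply is that the quoted 14.1 sentence also speaks of the study as a whole, that 14.5.1 has all adverse events captured on case report forms, and that 17.3 summarizes all of them. On that reading late events are recorded and counted. The general definition opening 14.3.1 has no day limit either; the reporting-period item is one entry in a list. This stands in part: the documents leave a longer reading open. But then 14.1 gives no end date and its 30-day clause does no work. The 30-day limit on concomitant medication in 10.1 supports the shorter reading.

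Other channels exist. 14.1 has the investigator notify the IRB of unanticipated, possibly related events after participation, and 14.5.16 sends events of special interest to the drug supplier within 15 calendar days of awareness. These narrow the gap in reporting. They do not place an expected, non-serious irAE in the 17.3 tables.

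Three stronger inferences are tempting and are not supported:

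- *That a 1-month visit after day 30 is itself a defect.* Onset date decides. An event that starts on day 25 and is elicited on day 42 belongs to the 30-day period, and a visit after day 30 is a sensible way to complete that period.
- *That patients held for toxicity lose most.* Visits and assessments continue on schedule during a hold (9.2, 11.1), and ongoing related events are followed past day 30.
- *That the end-of-treatment mismatch costs safety data.* Note 14 already asks for the visit on the decision day, and no lost data can be pointed to.

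**Conclusion.** The concern holds for new non-serious irAEs with onset on days 31–90. Under the 30-day rule they can be left out of a primary safety description, which biases irAE incidence downward relative to the 90-day follow-up the plan requires. The size is 4 points per affected patient, assuming 25 in the summary, with an unknown number affected.

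A reader might go further and conclude that late immune events are excluded outright, or that the trial's go/no-go conclusion is at risk. Neither follows: 17.3 states no exclusion, and the rule of 4 responses in 25 does not use these data. An incidence labelled as 30-day would be correct as such; the fault is that follow-up beyond day 30 has no matching collection rule and 17.3 names no window. The end-of-treatment limit is a minor matter of avoidable protocol deviations. The change is worth making because it is cheap and bears on a primary objective.

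**What to change.** - **14.1:** collect all adverse events to 30 days after the last dose, and suspected irAEs and all serious adverse events with onset to 90 days (+3) after it. Flag any event that starts after new anti-cancer therapy.
- **10.1:** record concomitant treatment given for those later events.
- **14.3.1 and 14.5.12:** refer to this period.
- **17.3:** tabulate all adverse events to day 30 and, separately, irAEs and serious events to day 90.
- **Note 14 and 7.5 (minor):** make end-of-treatment procedures due by day 21 after the last dose, or on the day of the decision to stop if that is later.

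Cost: no new visits or contacts, since follow-up to day 90 is already required; a few more adverse-event forms and wording edits in these sections. Later events are more confounded by disease and next-line therapy, which is why the flag and the separate table are needed.
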